8. TERMINATION OF THE STUDY

9. ADMINISTRATION AND REGULATORY CONSIDERATIONS

9.1 Prior to Initiation of the Study.....
9.2 Institutional Review Board.....
9.3 Informed Consent/Authorization.....
9.4 Duties of the Investigator.....
9.5 Monitoring.....
9.6 Study Records.....
9.7 Records Retention.....
9.8 Subject Privacy/Authorization.....

BRIEF ABSTRACT

INTRODUCTION: Pain is a common reason for individuals to seek health care, especially emergency care. Ketorolac has numerous advantages over other pain medications, especially the opioids. The intranasal administration of ketorolac has been shown to be safe and effective in the treatment of postoperative pain following major abdominal surgery and post dental surgery, but there have been no studies evaluating the use of intranasal ketorolac for the treatment of acute pain in the emergency department.

METHOD: Twenty-five adults who are in the ED for an acute episode of pain will receive a single dose of intranasal ketorolac. Their pain before and after receiving the ketorolac will be measured by pain scales e.g. the numeric rating scale (NRS). The efficacy will be assessed by several measures including pain relief, pain intensity difference, global pain evaluation, global assessment of analgesia, and the summed pain intensity difference (SPID). This will allow for assessment of meaningful pain relief and the time to pain relief. The safety will be assessed by documentation of adverse events, vital signs, and clinical assessment of the nasal mucosa before and after the intranasal administration of the drug. The efficacy, tolerability and safety will also be assessed by patient and health care provider questionnaires.

PRIMARY OBJECTIVES: To determine the efficacy of ketorolac in an acute care setting, the emergency department (ED).

SECONDARY OBJECTIVES: To determine the safety and tolerability of ketorolac in an acute care setting, the ED.

PATIENT POPULATION: Adults: 18- 64 years of age, previously healthy men and nonpregnant women, with acute pain (e.g. an acute orthopedic injury such as a fracture or a kidney stone) being seen in the emergency department.

INTERVENTION: Single dose of intranasal ketorolac

CLINICAL MEASUREMENT: Pain scale (numeric rating scale = NRS) will be completed before and after giving intranasal ketorolac. Pain relief (e.g. numeric pain scale), global pain evaluation, pain intensity differences, global anesthesia (global pain relief) and patient/health care questionnaires will be completed.

OUTCOME: Decrease in pain by several measures including NRS after intranasal ketorolac is given, tolerability and safety evaluation

INTRANASAL KETOROLAC FOR THE TREATMENT OF ACUTE PAIN IN THE EMERGENCY DEPARTMENT

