The rates of adverse events were similar in the two treatment groups (ketorolac 97.5% vs. placebo 98.0%) and were characteristic of events observed following major surgery and were not considered related to the study treatment in the majority 80%, (1150/1437) and were considered mild (72.9%). In the ketorolac group, nasal irritation (24.1% vs. 1.9%, $p < 0.0001$), throat irritation (7.0% vs. 0.9%) and lacrimation (7% vs. 0%) occurred more frequently in the ketorolac group than in the placebo group. Most events related to nasal irritation were mild, transient, and did not increase in severity with repeat dosing. Pyrexia was reduced in the ketorolac group (44% vs. 67%, $P = 0.001$). Serious adverse events were similar in both groups: 5 patients for ketorolac (2.5%), and 2 patients for placebo (1.9%). These were post-procedural hemorrhage (N=2), wound infection (N=1), wound complication (N=1), and wound secretion (N=1) for ketorolac and pain (N=1) and pleuritic pain (N=1) for placebo. The only serious event rated possibly related to study medication was the wound complication. There were no clinically relevant differences between the treatment groups regarding vital signs, hematology, or clinical chemistry measurements. No deaths occurred during the study.

Conclusion

Intranasal ketorolac was well tolerated and effective in treating moderate to severe postoperative pain in inpatients. The convenience of intranasal dosing suggests that its usefulness in the ambulatory care setting should be evaluated.

This was a single center, double-blind, randomized controlled study of 127 adult patients (N=42 placebo, N= 43 ketorolac 10 mg, N= 42 ketorolac 31.5mg) undergoing major surgery. Postoperative patients were randomized to either intranasal administration of placebo or ketorolac 10 mg or ketorolac 31.5 mg every 8 hours for 40 hours. The study drug was administered intranasally, giving 2 doses of 100 μ L of the study drug, with 1 dose (100 μ L to each nostril) via a metered device. Pain intensity was assessed after receiving the study drug. Patient controlled analgesia (PCA) was provided by supplemental morphine.

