2.1.2 Secondary Objective

To determine the safety and tolerability of intranasal ketorolac (sprix) in decreasing the acute pain of patients in the emergency department (ED)

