5.1.6.4 Safety Assessments

5.1.6.5 Site Assessments: Clinical

Site assessments (clinical) of the nasal passageways e.g. an examination of both nostrils) will be done before and after administration of the intranasal ketorolac (sprix). This will document that there is no changes in the nasal mucosa, etc. secondary to the administration of the intranasal drug (sprix).

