Appendix 2: Questionnaires

Appendix 2A: Patient Questionnaire

1. Did the intranasal pain medicine decrease your pain? yes _____ no _____
2. How effective was the intranasal pain medicine in decreasing your pain?
Mild decrease in pain __ Moderate decrease in pain __ Strong decrease in
pain _____
3. How satisfied were you with the use of the intranasal spray?
Very unsatisfied __ Unsatisfied _____ Satisfied __ Very satisfied _____
4. Would you consider using this intranasal pain medicine in the future when you
had pain? yes _____ no _____

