Appendix 2B: Health Care Provider Questionnaire

1. Was the patient successfully treated (had less pain) by using the spray?
yes __ no __
2. Did the patient have any unacceptable side effects from use of the spray?
yes __ no _____.
3. How satisfied How satisfied were you with the use of the intranasal spray?
Very unsatisfied __ Unsatisfied _____ Satisfied __ Very satisfied _____
4. Would you consider using this intranasal pain medicine in the future for your
patients who have acute pain? yes _____ no _____

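### The questionnaires are said to assess tolerability, but neither form asks directly about mild symptoms and no tolerability variable is defined

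*Combined protocol and SAP*

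**What the plan says.** The Brief Abstract (Method) first assigns safety to adverse events, vital signs and the nasal examination. It then adds: "The efficacy, tolerability and safety will also be assessed by patient and health care provider questionnaires". Section 2.1.2 makes safety and tolerability the secondary objective, and section 3.1 describes the study as an efficacy, safety and tolerability trial.

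The patient form (Appendix 2A) has four items. Two concern pain: "Did the intranasal pain medicine decrease your pain" and "How effective was the intranasal pain medicine in decreasing your pain". The third is "How satisfied were you with the use of the intranasal spray", and the fourth asks about willingness to use the product again. The provider form (Appendix 2B) has one item on side effects, answered yes or no: "Did the patient have any unacceptable side effects from use of the spray".

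Section 6.2.2 lists both questionnaires as secondary efficacy variables, and section 7.2 (Efficacy) is the only place that analyzes them. The safety variables in sections 2.2.3 and 6.3 and the safety analysis in 7.3 cover adverse events, vital signs and the nasal mucosa. None of them names a tolerability variable.

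Outside the questionnaires, sections 5.1.4 and 5.1.6.6 require side effects to be recorded, and the definition in 6.3.3.1 has no severity threshold. Sections 5.1.4.1 and 6.3.2 require the nasal mucosa to be examined before and after dosing.

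**The concern.** The plan names the questionnaires as a means of assessing tolerability, but their items cannot do that job. Satisfaction and future use touch on acceptability, but they mix it with pain relief: a patient whose pain fell and whose nose stung may well answer that they were satisfied. The provider item is limited by its own wording to unacceptable effects, so mild irritation would normally be answered no.

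This matters because the nasal route is what is new in this setting, and local irritation is the effect most specific to that route. Of the trial with the highest reported rate, section 1.2 says: "Most events related to nasal irritation were mild, transient, and did not increase in severity with repeat dosing". Effects of that kind are the ones that satisfaction items and an unacceptable-only item are least able to show. With no tolerability variable defined, that part of the secondary objective rests on adverse-event recording, for which the plan describes no question to the patient, and on a visual examination.

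**Working it through.** The plan gives no figure for tolerability. Its one calculated design figure, the sample size for the mean pain intensity difference (section 7.1), does not enter here; only the planned 25 patients are used.

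**Step 1. Compare the forms with the claim made for them.**

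| Item | What it measures | Can it record mild irritation? |
|---|---|---|
| 2A item 1 | pain decrease, yes/no | no |
| 2A item 2 | size of pain decrease | no |
| 2A item 3 | satisfaction with the spray | only indirectly, mixed with pain relief |
| 2A item 4 | future use | only indirectly, mixed with pain relief |
| 2B item 1 | treatment success (less pain) | no |
| 2B item 2 | unacceptable side effects | not if the effect is acceptable |
| 2B items 3 and 4 | provider satisfaction and future use | only indirectly |

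**Step 2. Check the other routes into the data.** Sections 5.1.4, 5.1.6.6 and 6.3.3.1 together make a side effect of any severity recordable on the case report form. They do not say whether the patient is asked or only volunteers it, and no severity grade is set. The nasal examination (5.1.4.1, 6.3.2) looks for visible signs such as redness or swelling. It does not cover throat or eyes, and its timing is fixed only as after dosing and before departure.

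**Step 3. Expected number of patients, 25 × rate (rates from section 1.2).**

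| Source | Dosing | Ketorolac | Placebo | 25 × ketorolac rate |
|---|---|---|---|---|
| Third-molar trial | single 31.5 mg | none reported (headache was the only ketorolac event) | none reported | 0 |
| Single-center major-surgery trial | 31.5 mg every 8 h for 40 h | 16.7% (7 of 42) | 11.9% (5 of 42) | 25 × 0.167 = 4.2 |
| Two-hospital phase 3 trial | 30 mg, single or repeat dosing up to 5 days | 24.1% | 1.9% | 25 × 0.241 = 6.0 |

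The phase 3 trial also reports throat irritation (7.0% vs 0.9%) and lacrimation (7% vs 0%): 25 × 0.07 = 1.75 patients each. At 16.7%, the probability of at least one irritation case among 25 is 1 − (1 − 0.167)^25 = 99.0%; at 24.1% it is 1 − (1 − 0.241)^25 = 99.9%.

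**Step 4. What provider item 2 alone would count.** The documents do not give the share of irritation that a provider would call unacceptable. Assuming 0%, 5%, 10% or 20%, at the 24.1% rate: 25 × 0.241 × share = 0, 0.3, 0.6 or 1.2 patients.

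**Step 5. Precision if irritation is asked about directly (Clopper-Pearson 95%).** 0 of 25: 0% to 13.7%. 4 of 25 (16%): 4.5% to 36.1%. 6 of 25 (24%): 9.4% to 45.1%.

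**The case against.** The strongest reply is that the questionnaires are only an additional source. Adverse events are the primary safety variable (2.2.3.1, 6.3.1), all side effects go on the case report form, and mild stinging or tearing meets the definition in 6.3.3.1. The 24.1% itself came from a trial that used spontaneous reports and clinical signs, so capture of that kind can detect mild irritation. The one cited trial of a single 31.5 mg dose reported only headache on ketorolac. The case report form is not among the documents, so it may prompt for nasal symptoms.

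All of this stands, and it limits the point. A reader might infer that mild irritation will be missed, or that a good tolerability result would only reflect the instruments. The documents do not support that: irritation has a recording route, and under-recording is possible but not shown. Nor should 24.1% be read as a single-dose or purely mild rate. It covers all nasal irritation in a trial that included repeat dosing, and only most of it was mild and transient.

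A reader might also infer from section 5.1.6.5 that the nasal examination presumes its result, because its purpose is worded as documenting that nothing changed. Sections 5.1.4.1 and 6.3.2 describe the same examination neutrally, so this is loose wording and not a design fault.

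The reply does not make the forms measure what the Brief Abstract says they measure, and it does not supply a tolerability variable. The third-molar trial also relied on spontaneous reports, so its silence on irritation cannot separate a true absence from an effect that was not volunteered. Unless patients are asked, this trial would face the same ambiguity.

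**Conclusion.** The mismatch is established from the text alone: the questionnaires are assigned tolerability, but they contain no direct symptom question and one side-effect item restricted to unacceptable effects, and they are classed and analyzed as efficacy measures only. No tolerability variable is defined anywhere.

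Its practical size is modest and uncertain. The cited rates imply about 0 to 6 of 25 patients with nasal irritation. The upper part of that range assumes that rates from postoperative trials that included repeat dosing carry over to one dose in the emergency department. The questionnaires as worded would show few or none of these patients; how many the case report form would show depends on whether they are asked, which the plan does not state. The change is worth making before enrollment because it is nearly free, and symptoms not asked about before departure are hard to recover. The evidence does not show that an extra nasal examination at a fixed time is needed, and none is proposed.

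**What to change.** 1. Add one item to Appendix 2A: *Did the spray cause irritation or discomfort of the nose, throat or eyes? none / mild / moderate / severe.*
2. Change Appendix 2B item 2 to ask about any side effect of the spray, with a follow-up on whether it was unacceptable.
3. Define the tolerability variable in section 6.3 as the proportion of dosed patients reporting irritation or discomfort on the new item. In section 7.3, report it by severity, with an exact 95% confidence interval for the overall proportion.

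Both forms are already completed before departure, so no new contact or procedure is needed. The cost is one extra line on each form. The downside is that a solicited rate is likely to be higher than a volunteered one. It will not be directly comparable with the rates in the two cited trials whose summaries state that adverse events were spontaneously reported (third-molar and phase 3); the report should say so.

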1. INTRODUCTION

1.1 Background

Pain is the number one reason for seeking health care. Patients are commonly seen in the emergency department (ED) with acute pain. Considering all ED visits, pain is the most common chief complaint. Up to 70% of ED visits are related to pain as the rationale for the ED visit.¹ Moreover, this does not include those individuals seeking care in urgent care centers, clinics or offices.

Ketorolac is effective in relieving pain. It has several advantages over other pain medications, including the opioids. First, since it does not bind to the opiate receptors (μ , κ , and δ), it is nonaddicting. However, a 30 mg dose of ketorolac given intramuscularly has a demonstrated analgesic effect between that obtained with morphine 6 mg and 12 mg. Next, it also has the additional safety advantage in that it avoids the side effects of the opioids including the fact that it does not cause respiratory depression or hypotension.

The intranasal route of administration has numerous benefits over other methods of drug administration. The intravenous (IV) route of drug administration is painful, takes time to establish, costs more to administer, and can have an initial high peak of drug effect (Tmax) which can have unwanted side effects/complications (e.g. rapid peak with an increased possibility of complications such as hypotension and respiratory depression).² The intramuscular route is also quite painful.² Orally administered medications take time to be absorbed and exert a maximal effect, have a variable absorption from the gastrointestinal tract, and may not be an option in patients with vomiting, diarrhea, mal-absorption or other gastrointestinal disorders.²

The intranasal route is easy to administer, is nonpainful (unlike an intramuscular shot or IV line insertion), has a rapid onset, and a more level or consistent efficacy over time with less of a sudden peak than IV and likely, lesser side effects/complications than IV.

2. Mace SE. Alternate routes for the systemic delivery of analgesics and sedatives. In: Mace SE, Ducharme J, Murphy MF (eds). Pain management and Sedation: Emergency Department Management. 1st ed. New York: McGraw-Hill Co, 2006; Ch. 47, pp. 366-380.

1.2 Summary of Clinical Studies with Intranasal Ketorolac

This was a double-blind, randomized controlled, multicenter (6 sites in the United States and New Zealand) trial in 321 adults (ages 18 to 64 years) undergoing major open abdominal surgery under general anesthesia. Patients were randomized to receive either intranasal ketorolac 31.5 mg or placebo, administered as one spray (100 µL) into each nostril, every 6 hours for the first 48 hours following surgery, then up to four times a day. After surgery, patients received intravenous opioid until they were comfortable. Then pain intensity (PI) ratings using a visual analog scale (VAS) of 0 to 100 mm where 0 represents no pain and 100 is the worst pain imaginable were done. When PI ratings were at least 40 on the VAS, patients received either intranasal ketorolac or placebo; in addition to patient access to intravenous morphine via patient controlled analgesia (PCA) through at least 48 hours for pain not controlled by the study drug.

Results: Efficacy

Mean pain intensity VAS scores were significantly lower in the intranasal ketorolac group compared to placebo at 20 minutes (55.4 ± 1.9 vs. 60.5 ± 1.3 , $p=0.014$), at 60 minutes (47.0 ± 1.5 vs. 53.5 ± 2.1 , $p=0.008$), 2 hours (43.3 ± 1.6 vs. 49 ± 2.2 , $p=0.026$), 3 hours (36.5 ± 1.5 vs. 44.2 ± 2.2 , $p=0.002$), 6 hours (29.8 ± 1.4 vs. 34.5 ± 2.2 , $p=0.0038$), 18 hours (29.0 ± 1.5 vs. 32.3 ± 2.3 , $p=0.016$), 24 hours (26.4 ± 1.5 vs. 32.3 ± 2.3 , $p=0.016$), and 30 hours (24.3 ± 1.5 vs. 29.5 ± 2.2 , $p=0.037$). The mean pain intensity difference (PID), calculated as the baseline VAS minus the post treatment VAS ($\text{PID} = \text{baseline VAS} - \text{post treatment VAS}$), was significantly higher for the ketorolac group than for the placebo at 20 minutes ($p=0.010$), 1 hour ($p=0.005$), 2 hours ($p=0.034$), and 3 hours ($p=0.017$). The 6 hour summed pain intensity difference (SPID6) was significantly higher for the intranasal ketorolac group compared to the placebo group least square means (\pm SE) $117.4 (\pm 7.7)$ vs. $89.9 (\pm 10.6)$, $p=0.032$; difference in means 27.6, (95% CI 2.5 – 52.7). The quality of analgesia was rated by patients (where 0 = poor, 1 = fair, 2 = good, 3 = very good, and 4 = excellent) as statistically better in the intranasal ketorolac group compared to the placebo group at all time points from 20 minutes to 24 hours except for the 40 minute and 6- hour time points. The global assessment of pain control was significantly better in the intranasal ketorolac group (where 0 = poor, 1 = fair, 2 = good, 3 = very good, and 4 = excellent), with the mean (\pm SE) being $2.6 (\pm 0.06)$ vs. $2.4 (\pm 0.09)$, $p=0.009$. The need for rescue medication was less for the intranasal ketorolac group than for the control. Morphine use was decreased by 34% for the 0 – 72 hours (82 mg vs. 121 mg), although the difference was not statistically significant because of a decreased need for analgesia with the use of intranasal ketorolac. All of this data indicates better analgesia with intranasal ketorolac than for the placebo group.

Results: Safety and Tolerability

The percent of patients with at least one adverse event were similar in the two treatment groups (ketorolac 93% (198/214) vs. placebo 96% (103/107). Adverse events were characteristic of those following major abdominal surgery. Common adverse events were nausea, constipation, vomiting, and headache. There was a trend ($\geq 5\%$ difference) for reduced incidences of nausea, constipation, pyrexia, and tachycardia in the ketorolac group compared to placebo. The majority of patients had mild adverse events with the proportion of adverse events similar in the ketorolac vs. the placebo group (84% vs. 79%). The rate of serious adverse events was identical at 6% in the two groups, of which 89% were considered not related to the study drug. Serious adverse events included: ileus, nausea and vomiting, post-procedural complications, and infections. No patient had gastrointestinal bleeding, surgical bleeding, or renal insufficiency considered related to the study drug.

Conclusion

Intranasal toradol was well-tolerated, provided effective pain relief within 20 minutes, and reduced the need for opioid analgesia use. “While intranasal ketorolac was assessed in an inpatient, conventional surgery setting in this study, intranasal ketorolac use may have more relevance for use in outpatient settings and ambulatory surgery or fast-track surgical procedures.”

This was a single center, double-blind, randomized controlled trial of 80 adult patients (≥ 18 years of age) undergoing third molar impaction surgery. Patients were randomized to receive either intranasal ketorolac (31.5 mg) or intranasal placebo. Efficacy was measured using summed pain intensity difference (SPID) score over the first eight hours after dosing (primary efficacy variable), and secondary efficacy variables: pain intensity (visual analog scale = VAS), total pain relief (TOTPAR) and global pain evaluation up to eight hours after dosing. Pain intensity was measured with a using a 100 mm VAS scale with 0 = no pain and 100 = worst pain possible. Pain intensity difference (PID) scores were calculated by subtracting each VAS post dose score from the baseline VAS score or $PID = \text{baseline VAS} - \text{post dose VAS}$. The SPID is calculated by taking a weighted sum of the PID scores.

The safety was assessed by assessing spontaneously reported adverse events and clinical signs, hematology and clinical chemistry throughout the treatment period and at a follow-up visit.

Results: Efficacy

The decrease in pain was significantly greater for the intranasal ketorolac than for the placebo. The results for intranasal ketorolac vs. intranasal placebo were mean (\pm SE) SPID8: 136.7 (\pm 33.0) vs. 105.2 (\pm 29.1), $p < 0.001$; SPID4: 90.3 (\pm 16.4) vs. 46.7 (\pm 13.5), $p < 0.001$; SPID6: 120.5 (\pm 24.7) vs. 76.7 (\pm 21.1), $p < 0.001$; TOTPAR4: 6.7 (\pm 0.8) vs. 1.7 (\pm 0.4), $p < 0.001$; TOTPAR6 9.7 (\pm 1.2) vs. 2.4 (\pm 0.7), $p < 0.001$; TOTPAR8: 12.0 (\pm 1.6) vs. 3.1 (\pm 0.9), $p < 0.001$. The time to perceptible pain relief (time to onset in minutes) was 21.5 for intranasal ketorolac vs. 480 for intranasal placebo, $p < 0.001$. The time to meaningful pain relief (time to onset in minutes) was 66.0 for intranasal ketorolac vs. 480 for placebo, $p < 0.001$. The need for rescue medication (minutes) was 360.0 for intranasal ketorolac vs. 95.5 for intranasal placebo, $p < 0.001$. The patient global assessment of pain control 8 hours after the intranasal ketorolac or placebo was also significantly better for ketorolac with a mean score of 1.9 ± 0.2 vs. 0.5 ± 0.1 , $p < 0.001$.

Results: Safety and Tolerability

More adverse events were reported in the placebo group (8 patients with 10 events) than in the ketorolac group (3 patients with 3 events). All events were mild or moderate in severity and no serious events were reported. Headache occurred in 8 subjects (placebo $n=5$; ketorolac $n=3$) and was the only adverse event in the ketorolac group. In addition to the headache, 3 patients in the placebo group reported nausea, 1 had vomiting, and 1 had dizziness. There were no clinically relevant differences between the treatment groups in clinical assessments at the follow-up visit.

Conclusion

A single 31.5 intranasal dose of ketorolac provided rapid and effective pain relief and was well tolerated in oral surgery patients for up to 8 hours

This was a two hospital, phase 3, double-blind, randomized controlled study of 300 adults ($N=199$ Ketorolac, $N= 101$ placebo) undergoing surgery (abdominal or orthopedic or breast reconstruction surgery). Post-operative patients were randomized to either 30 mg (100 μ l) intranasal ketorolac or intranasal placebo as a single dose or multidose regimen administered 3 times per day up to 5 days with backup analgesia as needed. Patients had access to morphine sulfate by patient-controlled analgesia (PCA). The primary efficacy endpoint was the single-dose summed pain intensity difference score (PID) at 6 hours. Secondary efficacy endpoints were pain intensity (PI) ratings using a visual analog scale (VAS) of 0- 100 mm where 0 represents no pain and 100 is the worst pain imaginable. PID scores were calculated by subtracting the post-treatment PI score from the baseline

score, where the baseline score was the PI rating made prior to the first dose of study medication on Day 1. SPID = Baseline PI – Post-treatment PI = Baseline VAS – Posttreatment VAS. The summed PID (SPID) was determined from weighted PID scores over 6 hours, where the weight is proportional to the time elapsed since the previous rating. Secondary endpoints included onset, peak effect, quality of analgesia, and duration of analgesia in the first 6 hours after single dose study drug administration. Onset of analgesia was determined by the patients clicking a stopwatch at the time they reached “meaningful” pain relief, where meaningful relief was defined as “relief that definitely makes you feel better”. Peak effect was the maximum PID score prior to restarting morphine sulfate by PCA. Quality of analgesia was rated using a five-point categorical scale where 0 = poor, 1= fair, 2 = good, 3 = very good, and 4 = excellent. The duration of analgesia was the time from the first dose of study medication on Day 1 to the first dose of morphine sulfate after restarting PCA. For the multidose regimen, efficacy assessments were global evaluation of pain control, mean total morphine sulfate use, and quality of analgesia ratings. The global assessment of pain control was rated by patients at the end of each day using a five-point categorical scale, where 0= poor, 1= fair, 2 = good, 3 = very good and 4 = excellent. Safety was assessed from spontaneously reported adverse events and measurement of adverse clinical signs. Hematology and clinical chemistry measurements were made at the termination visit, which occurred between 4 and 9 days after the start of dosing.

Results: Efficacy

The SPID6 score was significantly higher for the ketorolac group than for the placebo group. The mean (\pm SE) was 83.8 (\pm 10.6) for ketorolac vs. 37.2 (\pm 12.9) for the placebo $p=0.007$. For the single-dose group, the mean PID scores through 6 hours were significantly higher for subjects in the ketorolac group than the placebo group at every time point (1/2, 1, 2, 3, 4 hours). Both the peak relief and the maximum PID score prior to restarting the PCA were significantly higher in the ketorolac group compared to the placebo group. For the single dose regimen, the quality of analgesia was significantly better for the ketorolac group compared to the placebo group at 1/2, 1, 2, 3, 4, and 5 hours and approached significance at 6 hours. The duration of analgesia was significantly longer in the ketorolac group vs. the placebo group, as denoted by the time to restarting PCA or requesting rescue medication (3 vs. 1.3 hours, $p < 0.04$). A significantly greater proportion of patients in the ketorolac group reported meaningful pain relief compared to placebo at 1 and 1.5 hours ($p < 0.05$) and approached statistical significance at 2 hours. Morphine use was significantly lower in the ketorolac group compared with the placebo group for all time intervals ($p < 0.001$). The mean (\pm SE) morphine use for ketorolac vs. placebo was 34.0 (\pm 1.64) vs. 48.4 (\pm 2.93) on day 1, 18.8 (\pm 11.51) vs. 29.2 (\pm 2.61) for day 2, and 51.4 (\pm 2.75) vs. 77.4 (\pm 5.28) for days 1 and 2. The global pain assessment was significantly better for the ketorolac group than the placebo group on days 3 and 4. The quality of analgesia rating was significantly higher at the 8 hours in the ketorolac group vs. the placebo group at 8 hours: 2.9 (\pm 0.06) vs. 2.6 (\pm 0.1), $p=0.011$).

Results: Safety

The rates of adverse events were similar in the two treatment groups (ketorolac 97.5% vs. placebo 98.0%) and were characteristic of events observed following major surgery and were not considered related to the study treatment in the majority 80%, (1150/1437) and were considered mild (72.9%). In the ketorolac group, nasal irritation (24.1% vs. 1.9%, $p < 0.0001$), throat irritation (7.0% vs. 0.9%) and lacrimation (7% vs. 0%) occurred more frequently in the ketorolac group than in the placebo group. Most events related to nasal irritation were mild, transient, and did not increase in severity with repeat dosing. Pyrexia was reduced in the ketorolac group (44% vs. 67%, $P = 0.001$). Serious adverse events were similar in both groups: 5 patients for ketorolac (2.5%), and 2 patients for placebo (1.9%). These were post-procedural hemorrhage (N=2), wound infection (N=1), wound complication (N=1), and wound secretion (N=1) for ketorolac and pain (N=1) and pleuritic pain (N=1) for placebo. The only serious event rated possibly related to study medication was the wound complication. There were no clinically relevant differences between the treatment groups regarding vital signs, hematology, or clinical chemistry measurements. No deaths occurred during the study.

Conclusion

Intranasal ketorolac was well tolerated and effective in treating moderate to severe postoperative pain in inpatients. The convenience of intranasal dosing suggests that its usefulness in the ambulatory care setting should be evaluated.

This was a single center, double-blind, randomized controlled study of 127 adult patients (N=42 placebo, N= 43 ketorolac 10 mg, N= 42 ketorolac 31.5mg) undergoing major surgery. Postoperative patients were randomized to either intranasal administration of placebo or ketorolac 10 mg or ketorolac 31.5 mg every 8 hours for 40 hours. The study drug was administered intranasally, giving 2 doses of 100 μ L of the study drug, with 1 dose (100 μ L to each nostril) via a metered device. Pain intensity was assessed after receiving the study drug. Patient controlled analgesia (PCA) was provided by supplemental morphine.

The subjects rated their pain on a 100 mm visual analogue scale (VAS) where 0= no pain and 100 = worst pain possible. The pain intensity difference (PID) was calculated by subtracting the post study drug VAS from the baseline (pre-study drug) VAS or $PID = \text{post-study drug VAS} - \text{baseline VAS}$. The summed PID (SPID) was calculated by adding the weighted PID scores over the time intervals.

Outcome measures: The primary outcome measure was the total morphine use by PCA pump in the first 24 hours. Secondary outcome measures were total morphine use for first 2 days (48 hours) and total morphine use on day 2 (24 to 48 hours)

Results: Efficacy

The analgesic response was significantly greater for the 31.5 mg ketorolac group compared with the placebo for day 1, day 2 and the 48-hour morphine use, and for the 4-hour and 6 hour SPID. The 10 mg ketorolac groups also demonstrated a better analgesic response than for the placebo, but the difference was not statistically significant. The mean morphine consumption for the 3 groups was day 1 post-op: placebo 56.5 mg, 10 mg ketorolac 54.3 and 31.5 mg ketorolac 37.8 mg ($p=0.0013$), day 2 placebo 32.6 mg, 10 mg ketorolac 28.3 mg, and 31.5 mg ketorolac 23.11 mg ($p=0.0182$), and for the 48 hours post-op: placebo 87.9 mg, 10 mg ketorolac 78.7 mg, and 31.5 mg ketorolac 61.4 mg ($p=0.0060$). The 4 hour SPID was 75.9, 10 mg ketorolac 89.6, and 31.5 mg ketorolac 120.1 ($p=0.0017$). The 6 hour SPID was placebo 130.6, 10 mg ketorolac 154.8, and 31.5 mg ketorolac 195.5 ($p=0.0015$).

Results: Safety

The frequency of adverse events for the 3 groups was placebo 97.6%, 10 mg ketorolac 100%, and 31.5 mg ketorolac 95.2%. Most adverse events were mild or moderate. The most common adverse events were pyrexia and nausea, both occurring in 50.4% overall. Pyrexia was significantly less common ($p=0.0088$) in the 31.5 mg ketorolac group than in the placebo group, with pyrexia reported in 33.5% of the 31.5 mg ketorolac group, in 55.8% of the 10 mg ketorolac group and in 61.9% of the placebo group. Tachycardia was significantly less frequent in the 31.5 mg ketorolac group than the placebo group ($p=0.0317$). The frequency of tachycardia in the 3 groups was placebo 40.5%, 10 mg ketorolac group 16.3%, and 31.5 mg ketorolac group 19.0%. Pruritus was less frequent in the ketorolac groups than placebo but the difference was not statistically significant ($p=0.0790$). The frequency of pruritus was placebo 23.8%, 10 mg ketorolac 18.6%, and 31.5 mg ketorolac 9.5%. Adverse events typically associated with NSAID use (i.e. abdominal pain, dyspepsia, hematemesis, fluid retention, and oliguria) were all reported by three or fewer subjects in each group. Nasal irritation was reported in the following frequencies: placebo 11.9% (5 subjects), 10 mg ketorolac group 14.0% (6 subjects), and 31.5 mg ketorolac group 16.7% (7 subjects). The frequency reported for epistaxis was placebo 2.4% (1 subject), 10 mg ketorolac 2.3% (1 subject), and 31.5 mg ketorolac 7.1% (3 subjects). All events were mild or moderate in intensity.

Conclusion

Intranasal ketorolac in a 31.5 mg dose demonstrated significant analgesic efficacy compared to placebo and 10 mg of ketorolac.

1.3.Risk – Benefit

Ketorolac has value as a medicine to relieve pain. Ketorolac has numerous advantages over other classes of analgesics, especially opioids. Since ketorolac does not bind to opiate receptors, it is nonaddicting and avoids the side effects of the opioids.³ Therefore, some of the advantages include: lesser incidence of respiratory depression, lesser incidence of hypotension, lesser incidence of constipation, and no danger of addiction. Multiple studies have demonstrated the benefit of ketorolac as a medication to decrease

or eliminate pain. Ketorolac has been proven effective for pain relief, especially for certain types of pain; such as musculoskeletal pain, headaches and the pain from renal colic. In appropriate patients; ketorolac is a relatively safe drug for the treatment of pain.⁴⁻⁶ Side effects and complications, such as gastrointestinal complaints (e.g. abdominal pain, dyspepsia, GI bleeding) and renal dysfunction (elevation of the BUN and creatinine) have been reported but with appropriate patient selection are uncommon or rare. The use of NSAIDS including ketorolac is not recommended in patients with active peptic ulcer disease, renal disease or at risk for renal failure due to volume depletion, cerebrovascular bleeding, hemorrhagic disorders, or those with a high risk of bleeding. With appropriate patient selection, ketorolac can be a safe and effective medication for the relief of pain.

3. Highlights of prescribing information. Distributed by American Reagent, Inc. Shirley, NY 1967.
5. Cordell WH. Renal (ureteral) colic. In: Mace SE, Ducharme J, Murphy MF (eds). *Pain management and Sedation: Emergency Department Management*. 1st ed. New York: McGraw-Hill Co, 2006; Ch. 36, pp. 261- 268.3.
6. Kelly A. Headaches. In: Mace SE, Ducharme J, Murphy MF (eds). *Pain management and Sedation: Emergency Department Management*. 1st ed. New York: McGraw-Hill Co, 2006; Ch. 38, pp. 261- 268.3, pp.279-285.

